**9.2.3. Toxicity Profile of Oral Retinoids (Class Effect):**

The safety profile of IRX5183 may correspond with the characteristic profile of systemic RAR agonists (ATRA [tretinoin], 13-*cis*-retinoic acid [isotretinoin], acitretin and etretinate) currently in use for acute promyelocytic leukemia (APL), acne, and psoriasis.

The most frequently reported adverse events in this drug class include headache, fever, skin/mucous membrane dryness, bone pain, nausea/vomiting, rash, mucositis, pruritus, increased sweating, visual disturbances, ocular disorders, alopecia, skin changes, changed visual acuity, bone inflammation, and visual field defects.

Headache occurring several hours after drug ingestion is also a common side-effect. Mild analgesics generally suffice for control and the patient usually develops a tolerance to the effect. Bone pain occurs in 10% to 20% of patients and usually remits with continued treatment: occasionally narcotic analgesia may be required to overcome the pain. Skin and mucous membrane effects can be managed with topical lubricants.

Pseudotumor cerebri, a known consequence of Vitamin A toxicity, has been documented in several patients. These persons have required serial lumbar punctures, high dose corticosteroids, and narcotic analgesics.

The following table summarizes the characteristic toxicities associated with the use of oral retinoids (De Vita Jr VT, 1997; *Physician's Desk Reference*, 2000).

**Table 4: Toxicities reported with the use of oral retinoids**

Cardiovascular effects	Peripheral edema, episodic hypotension, arrhythmias, flushing, edema
Central nervous system effects	Headache, intracranial hypertension (“pseudo tumor cerebri”), fever, fatigue, anxiety, confusion, dizziness, malaise, weakness, insomnia, rigors, paresthesias, depression psychosis
Gastrointestinal effects	Abdominal pain, vomiting, nausea, constipation, diarrhea, nonspecific bowel disorders, weight loss, weight gain, dyspepsia
Gynecologic effects	Increased menstrual bleeding
Hematological effects	Bleeding in other areas
Endocrine effects	Hypertriglyceridemia, hypercholesterolemia, increased LDH, hypercalcemia, hepatic toxicity (raised SGOT, SGPT, bilirubin, alkaline phosphatase), elevated sedimentation rates, elevated CPK, decreased WBC or RBC, and increased WBCs in urine
Musculoskeletal effects	Arthralgias, myalgias, bone pain, skeletal hyperostosis, weakening of the bones or abnormal bony growths
Ophthalmologic effects	decreased night vision, dry eyes, visual field defects, changes in visual acuity, visual disturbances, ocular disorders
Renal effects	Abnormal kidney function, nonspecific findings of the urinary or genital tract
Respiratory effects	Dyspnea, infections, chest discomfort
Skin or mucous membranes	Skin/mucous membrane dryness, skin fragility, rash, pruritus, dry mouth, mucositis, dry lips, and nose, cheilitis, epistaxis, peeling of the palms and soles, sticky skin, increased sweating, sensitivity to the sun, changes in skin pigment, other skin disorders, hair thinning and other hair disorders, nail disorders and genital excoriations
Special senses effects	Ringling in the ears, earaches
Teratogenic effects*	Spontaneous abortion, birth defects

\*See section on teratogenic effects above

#### 9.2.4. Differentiation syndrome (DS):

DS is a common occurrence in patients with APL treated with ATRA. The syndrome has been defined by the presence of the following signs or symptoms: unexplained fever, dyspnea, pleural and/or pericardial effusion, pulmonary infiltrates, renal failure, hypotension, and unexplained weight gain greater than 5 kg, and graded based on the number of these findings (Montesinos et al., 2009). Patients with 4 or more of the aforementioned signs or symptoms are classified as having severe DS, whereas those with 2 or 3 signs or symptoms are classified as having moderate DS. This condition is best treated with high dose dexamethasone at a dose of 10 mg IV twice daily.

Grade 1 DS per CTCAE v4 is defined as “fluid retention; <3 kg of weight gain; intervention with

fluid restriction and/or diuretics indicated.” Grade 2 is defined as “moderate signs or symptoms; steroids indicated.” Grade 3 is defined as “severe symptoms; hospitalization indicated.” Grade 4 is defined as “life-threatening consequences; ventilator support indicated.” The definition per CTCAE is “a disorder characterized by weight gain, dyspnea, pleural and pericardial effusions, leukocytosis and/or renal failure originally described in patients treated with all-trans retinoid acid.”

## 10. STUDY CALENDAR

Baseline evaluations are to be conducted within 14 days prior to start of protocol therapy (first dose of IRX5183). In the event that the patient’s condition is deteriorating, laboratory evaluations should be repeated within 48 hours prior to initiation of therapy. An interim history and physical should be done with each visit. IRX5183 will each be administered on a daily basis with one cycle consisting of 28 days (4 weeks).

Complete blood counts with WBC differential and blood chemistries will be measured twice weekly during the first cycle of treatment, at least weekly throughout the second cycle of therapy, at least every other week during consolidation/maintenance, and at least monthly during extended maintenance, or as often as clinically indicated. Fasting lipids with triglyceride evaluation will occur q2 weeks through the first month and then q8 weeks subsequently, per standard of card assessment on retinoid therapy.

Treatments and Evaluations ▲	Pre-Study	Cycle 1:				Cycle 2:				Cycles 3-6: 				End of Study
		W1 D1&4	W2 D1&4	W3 D1&4	W4 D1&4	W1 D1	W2 D8	W3 D15	W4 D22	W1 D1	W2 D8	W3 D15	W4 D22	
IRX5183 (daily)		X	X	X	X	X	X	X	X	X	X	X	X	
Informed consent	X													
Adverse Events and Toxicity Reporting	X	X X	X X	X X	X X	X	X	X	X	X	X	X	X	X**
Medical history	X	X	X	X	X	X		X		X		X		X##
Physical exam	X	X	X	X	X	X		X		X		X		X##
Height	X													
Transfusion Review	X	X X	X X	X X	X X	X	X	X	X	X		X		
Weight	X	X		X		X		X		X		X		
ECOG Perform Status	X	X	X	X	X	X	X	X	X	X	X	X	X	
FACTleu questionnaire	X								X*				X*	
CBC w/ diff., plts	X	X X	X X	X X	X X	X	X	X	X	X		X		
Comprehensive Panel	X	X X	X X	X X	X X	X	X	X	X	X		X		
Fasting Lipid Panel 	X		X		X								X	
Urine Pregnancy	X													
JH Path Review of Diagnosis	X#		X#			X#			X#				X#	X
Peripheral Blood for Research	X#		X#			X#			X#				X#	X
Pharmacokinetics		X♦	X♦			X♦								

Bone Marrow Aspirate Biopsy 	X#		X#		X#		X#		X#	X
--	----	--	----	--	----	--	----	--	----	---

 If minimal toxicity and at least SD, patients will have the option of continuing on therapy past 6 cycles, for up to an additional year of extended maintenance therapy. At that point, patients will have blood tests at least monthly and will complete a bone marrow biopsy after every 4 cycles of treatment. If the patient doesn't continue on for additional cycles past 6, follow-up in terms of blood counts will be completed per standard guidelines for AML monitoring as clinically indicated.

 Evaluations will continue to occur q8 weeks following cycle one.

 Patients may have a planned 5-7 day "rest" period between each cycle where patients are scheduled to undergo response assessment by bone marrow sampling (except for after cycle 1). Patients may start their next scheduled cycle of therapy once the marrow testing is completed but no longer than 42 days from the initiation of the previous cycle.

\* To be done at the completion of the 2nd cycle and then at the completion of the 6th cycle.

\*\* Patients will be monitored for toxicity at least 30 days post last dose of study drug.

# To be done at baseline, day 14 ( $\pm$  3 days) of cycle 1, after completion of cycle 1, 2, 4, 6, 10, 14, and 18, and at the end of the study.

## Patients will be monitored at least monthly for 6 months after study completion in person, or by phone if patient followed by a local oncologist.

◆ Draw ½ hour before the morning dose and then 2 hours ( $\pm$ 30 minutes) post drug administration on days 1 and 14 ( $\pm$  3 days). On day 14 ( $\pm$  3 days), bone marrow will be obtained for PK about 2 hours post drug (allowed as soon as 1 hour or as long as 4 hours post). May be obtained post cycle 1, only if day 14 BM specimen not available.

▲ Variations of  $\pm$  3 days of the scheduled visit are permitted. Labs may be drawn more frequently if clinically indicated.

An unscheduled visit can occur at any time during the study. The date for the visit and any data generated must be recorded on the appropriate CRF. Source documents for these unscheduled visits must also be maintained.

Pregnancy tests are only for females of childbearing potential. A female of childbearing potential is a sexually mature female who: 1) has not undergone a hysterectomy or bilateral oophorectomy; or 2) has not been naturally postmenopausal for at least 24 consecutive months (i.e., has had menses at any time in the preceding 24 consecutive months).

## 11. STATISTICAL CONSIDERATIONS

### 11.1. Study design & endpoints:

In the dose-escalation part of the study, there will be 3 dose levels (dose level 1 [DL1] with 50 mg, DL2 with 75 mg, and DL3 with 100 mg), with 1 additional dose level to be only used if excessive toxicity noted at the DL1. There will be no intra-patient dose escalation. Dose-escalation rules are defined through a standard 3+3 algorithm as outlined in Section 5.2.

The phase II expansion part of the study will aim to recruit a total of 27 patients with either R/R-AML or HR-MDS, and there will be an interim analysis after 13 patients for futility through a Simon two-stage minimax design based upon a Type I error rate of 0.05, power of 0.8, response probability of poor drug 0.05, and response probability of good drug of 0.2, based on prior relapsed and refractory AML trials and CTEP data on non-pediatric oncology trials from 2001 to 2012 (Itzykson et al., 2015; Ritchie et al., 2013; Thol et al., 2015; Yoko Korenaga Fukuda, 2014). Stage 1 will enroll 13 patients at the RP2D and will require at least 1 response for

continued enrollment to Stage 2, to reach the total of 27 patients. A total of 4 or more responses out of 27 patients will be considered encouraging evidence for future larger clinical trials of IRX5183.

Response will be defined per IWG criteria as CR, CRi, or PR for AML patients and as CR, CRi, PR, or HI for MDS patients (see definitions in Appendix A) and will be determined with each BM assessment. The composite of these responses across our study population will be referred to as the overall response rate (ORR). Rates of CR, CRi, PR, HI, and the composite endpoint of ORR will be summarized and reported with an exact 95% confidence interval.

### **11.2. Primary endpoints:**

1) Phase I - description of toxicity of IRX5183 by grading and tabulation using NCI-CTC Version 4.0 criteria (section 8). The DLT will be defined as per section 5.2.

2) Phase II – best response after at least 2 cycles of therapy per IWG criteria (**Appendix A**).

### **11.3. Secondary endpoints:**

1) Phase I - Description of PK parameters of IRX5183 at baseline and day 14, both in the peripheral blood and BM compartments, markers of myeloid differentiation by flow cytometry (e.g. CD15, CD11b), BM blast count, ANC before and after treatment, and changes in detectable cytogenetic abnormalities in the blood and BM compartments at the different dose levels. We will also describe best response per IWG criteria at any time, time to first and best response, and clinical parameters such as transfusion requirements, blood counts, quality of life assessments, and time to either progression or death.

2) Phase II – Description of IWG response and other clinical criteria assessed in the dose escalation phase for the RP2D. We will also measure markers of differentiation assessed in the dose escalation phase for the RP2D, and lastly, the toxicity profile at the RP2D dose.

### **11.4. Sample size considerations:**

For the dose-escalation part of the trial, we will enroll up to 18 patients, per standard 3+3 design with 3 DLs (see table 2 in section 5.2). Once we have determined our RP2D, we will proceed to phase II of the trial, where we will recruit an additional 21 R/R-AML or HR-MDS patients at the RP2D, for a total sample size at the RP2D of 27 (inclusive of patients treated at the RP2D in phase I). This sample size was determined using a minimax Simon two-stage design, as described in Section 11.1. Based on prior experience at our institution in this patient population, we will account for a dropout rate of 30%, so we will aim to recruit an additional 8 patients to the dose expansion phase, so that our trial will accrue up to 35 patients to this phase.

In phase II of the trial, the study team will meet regularly to determine whether it is worthwhile to continue enrollment, if an excessive number of patients are unable to complete 2 full cycles of therapy at the RP2D, whether for reasons of DLTs or PD.

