**Study Phase II:**

The phase II part of the study will use the optimal dose identified in the phase I part of the study and will aim to recruit a total of 27 patients with AML and HR-MDS at the RP2D (see sample size calculation in section 11). The primary goal of the therapy in this phase of the trial is to determine response after receiving at least 2 cycles of therapy per IWG criteria. Analysis of clinical response will take place after the first 13 patients complete induction therapy, and enrollment will continue to the planned 27 patients if the first stage has at least 1 patient achieve a CR or CRi or PR (AML) or CR or PR or HI (MDS). We will halt enrollment after the first 13 patients complete induction therapy until we have their response data. In addition to IWG response, many secondary endpoints will be assessed as outlined in section 11 below.

**Figure 2: IRX5183 Administration Schema.** Induction phase will consist of 56 days of oral IRX5183 daily. Consolidation/maintenance phase will begin once patient has confirmed SD or better and will continue for up to four 28-day cycles. If patient is in CR after consolidation/maintenance, will hold therapy and monitor, and resume therapy if they relapse. If they have SD or better after consolidation/maintenance, they will continue on maintenance therapy for up to 1 additional year. Select patients may be eligible to continue for longer.

**Table 1: Dose Escalation of oral IRX5183 administration in phase I part of the study.** \*: DL(-1) will only recruit if the maximally

administered dose was reached at DL1. DL: dose level.

Dose level (DL)	Daily dose (mg)
DL(-1)*	25
DL1	50
DL2	75
DL3	100

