### **11.8.2. Evaluation of response:**

All patients included in the study that complete 2 cycles of therapy will be assessed for response to treatment, even if there are major protocol treatment deviations or if they are ineligible. The primary endpoint to the dose expansion phase is response per IWG criteria after receiving at least 2 cycles of therapy. Only those patients who have measurable disease present at baseline, have received at least 2 cycles of therapy, and have had their disease re-evaluated will be considered evaluable for response. These patients will have their response classified according to the definitions stated in Appendix A. Patients who exhibit objective disease progression prior to the end of cycle 2 will be considered not evaluable and will be taken off study.

An incorrect treatment schedule or drug administration does not result in exclusion from the analysis of the response rate. Patients with disease progression, death due to their disease, and death due to toxicity prior to completion of induction therapy will be excluded from the primary analysis. This will prevent dismissal of an active drug based on progression in patients with highly refractory disease who are unable to receive enough of the drug to see a clinical benefit. Patients who are unable to complete induction therapy for any reason will be treated as missing data and additional patients will be recruited in their place to reach our target sample size of 27 for phase II.

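### Section 11.4 takes its 30% dropout allowance as 30% of the 27 evaluable patients; the resulting 35 covers only 22.9% loss, and 30% implies about 39

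*Combined protocol and SAP*

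**What the plan says.** Section 11.4 (Sample size considerations) fixes the phase II size: "we will recruit an additional 21 R/R-AML or HR-MDS patients at the RP2D, for a total sample size at the RP2D of 27", a total described as "inclusive of patients treated at the RP2D in phase I". The difference, 27 − 21 = 6, is the number carried over from phase I. It then adds the dropout allowance: "we will account for a dropout rate of 30%, so we will aim to recruit an additional 8 patients to the dose expansion phase". The accrual figure drawn from this is worded as an upper limit: "so that our trial will accrue up to 35 patients to this phase".

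Section 11.8.2 (Evaluation of response) defines who counts. Only patients with measurable disease at baseline who "have received at least 2 cycles of therapy, and have had their disease re-evaluated will be considered evaluable for response". On non-completers it says: "Patients who are unable to complete induction therapy for any reason will be treated as missing data". The same sentence provides for their replacement: "additional patients will be recruited in their place to reach our target sample size of 27 for phase II". Section 5.1 (Study Phase II) counts the first stage the same way: "Analysis of clinical response will take place after the first 13 patients complete induction therapy".

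So 27 is a number of evaluable patients, and 35 is the number accrued to obtain them.

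**The concern.** A dropout rate is a fraction of the patients who enter. To keep 27 after losing 30%, one divides 27 by 0.70. Section 11.4 instead multiplies 27 by 0.30 and adds the result, so the allowance is smaller than the rate it is said to cover.

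There are two related difficulties. First, it is unclear what 35 counts. The sum 27 + 8 = 35 includes the phase I patients at the RP2D, yet the text assigns 35 to the expansion phase, where the new patients it lists are 21 + 8 = 29. Second, the figure is worded as an upper limit, while Section 11.8.2 replaces every non-completer until 27 is reached. Both can hold only if no more than 8 of 35 are lost. No passage says explicitly that accrual may exceed 35.

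At stake is the accrual number on which timelines and other planning rest and, if someone treats 35 as a ceiling, the power of the phase II test.

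**Working it through.** **Inputs.** Evaluable target 27, of whom 21 new; dropout 30%; 8 added; 35 accrued (all Section 11.4). Stage 1 of 13 patients, continue with at least 1 response; success with at least 4 of 27; response rates 0.05 and 0.20 (Section 11.1). Evaluability and replacement (Section 11.8.2). Up to 18 phase I patients (Section 11.4); up to 3 patients per month over 12–18 months (Section 11.5).

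**Base sample size.** The exact two-stage calculation gives power 0.8011 at 0.20 and type I error 0.0416 at 0.05. The 27 reproduces as the minimax design.

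**The plan's allowance.** 27 × 0.30 = 8.1, taken as 8; 27 + 8 = 35. The stated figures reproduce this way.

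**What 35 covers.** 8/35 = 22.9%. At 30% loss, 35 × 0.70 = 24.5 evaluable patients are expected.

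**What 30% requires.**
- Loss possible in all patients at the RP2D: 27/0.70 = 38.6, about 39, which is 4 more than 35.
- Six phase I patients already known to be evaluable, loss only among new patients: 6 + 21/0.70 = 36, which is 1 more than 35.

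**Replacement until 27 are evaluable.** Each patient is assumed to complete independently with probability 0.70. The chance that a given accrual suffices is P(Bin(N, 0.70) ≥ 27), or P(Bin(N − 6, 0.70) ≥ 21) when six are secured.

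| Accrued at RP2D | Loss in all patients | Six already evaluable |
|---|---|---|
| 35 | 0.23 | 0.48 |
| 36 | 0.33 | 0.59 |
| 39 | 0.62 | 0.84 |
| 42 | 0.84 | – |
| 44 | 0.92 | – |

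**If 35 were a hard cap.** The threshold stays at 4 responses and the evaluable number is truncated at 27. Power at 0.20 is 0.779 with 26 evaluable, 0.755 with 25 and 0.727 with 24. Averaged over the binomial number evaluable:

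| Reading of 35 | Expected evaluable | P(at least 27) | Average power |
|---|---|---|---|
| 35 in total | 35 × 0.70 = 24.5 | 0.23 | 0.73 |
| Six evaluable + 29 new | 6 + 29 × 0.70 = 26.3 | 0.48 | 0.77 |
| 35 new + six, loss in all 41 | 41 × 0.70 = 28.7 | 0.78 | 0.79 |
| 35 new + six evaluable | 6 + 35 × 0.70 = 30.5 | 0.93 | 0.80 |

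**Accrual time.** This assumes phase I uses all 18 patients, six of them at the RP2D.
- 35 at the RP2D: 18 + 35 − 6 = 47 patients; 47/3 = 15.7 months at the maximum rate; 47/18 = 2.61 per month needed to finish in 18 months.
- 39 at the RP2D: 18 + 39 − 6 = 51 patients; 51/3 = 17.0 months; 51/18 = 2.83 per month.

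Neither time includes the 28-day wait after the first 3 patients of each cohort or the enrolment halt after stage 1.

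**The case against.** The strongest reply is that the plan already deals with dropout where it matters. Section 11.8.2 replaces non-completers and Section 5.1 counts stage 1 by completers, so the evaluable number, decision rules, type I error and power do not depend on 35. That stands, and it is why the point is minor. Section 11.4 also has the study team meet regularly to reconsider enrolment if too many patients fail to complete two cycles. That is a real safeguard, but it neither corrects the 8 nor says which rule prevails.

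A second reply is that the gap depends on what 35 means. Read as 35 new patients on top of six, the total is 41, which tolerates 14/41 = 34% loss, so there is no shortfall. That reading fits poorly with the plan's own 21 + 8 = 29. If dropout touches only the 21 new patients, the gap is a single patient. The plan does subtract six from 27, which gives this reading some footing, but it does not say those six are known to be evaluable: the phase I DLT check falls at 28 days, whereas evaluability needs two cycles.

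A third reply is that the hard-cap power figures describe a rule the trial has not adopted. That is correct. They show what the ambiguity could cost and should not raise the severity. Nor is a timeline overrun shown: 17.0 months lies inside the stated window.

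**Conclusion.** The concern holds as a minor arithmetic error. The allowance covers 22.9% loss, not 30%. The accrual figure at the RP2D is about 4 patients too low when 35 is the total and loss can fall on any patient, and 1 too low if six phase I patients are already secured. On the natural reading, in which replacement governs, the Simon design is unaffected. At the plan's own 30% rate, the 35 and the replacement rule will probably, though not necessarily, collide: 35 suffices with probability 0.23, or 0.48 with six secured. A material loss of power, about 0.07 against 0.801, arises only if 35 is a hard cap on the total and the threshold of 4 is kept; under the other three hard-cap readings the loss is about 0.03 or less.

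These results take the 30% rate as given and assume independent losses at that rate.

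**What to change.** In Section 11.4, give the expected accrual at the RP2D under 30% dropout as 39 (27/0.70), or as 36 (6 + 21/0.70) if phase I patients are counted only once known to be evaluable. Say whether the figure includes the phase I patients. Label it a planning expectation, since even 39 suffices only 62% of the time when loss can fall on all patients, and add a clause to Section 11.8.2 that replacement prevails over it. If 35 is meant as a hard cap, say so and state the expected evaluable number and power for the chosen reading.

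The cost is a text change. It adds no patients beyond those the replacement rule already implies. Section 11.5 may need a matching check: 51 patients leave one month of the 18 even at the maximum rate, and accrual of 44 at the RP2D would take (18 + 44 − 6)/3 = 18.7 months, in both cases before the protocol's built-in waits.

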### **Study Phase I:**

In the dose-escalation part of the study, we will abide by a traditional 3+3 design with 3 dose levels (dose level 1 [DL1] with 50 mg IRX5183, DL2 with 75 mg, and DL3 with 100 mg), with 1 additional dose level, DL(-1), to be only used if excessive toxicity is noted at the DL1. There will be no intra-patient dose escalation.

The first patient will enter the trial on DL1. The dose for level 1 will be a flat dose of 50 mg IRX5183 daily per the schedule above. We will enroll 3 patients at a time to determine the toxicity profile of IRX5183. If none of the 3 patients receiving DL1 experiences a DLT, another 3 patients will be treated at the next higher dose level. However, if 1 of the first 3 patients experiences a DLT, 3 more patients will be treated at the same dose level. The dose escalation will continue until at least 2 patients among a cohort of 3 to 6 patients experiences DLTs. If 2 or more patients experience a DLT on DL1, the next patient will be recruited to DL(-1). The RP2D of single agent IRX5183 will generally be the highest dose at which the DLT rate is <33% in at least six patients. If no MTD is determined, the highest dose

[figure not shown]
explored will be 100 mg. At the end of phase I, the RP2D will be determined after careful review of all of the clinical data available. The first 3 subjects enrolled to any cohort must have passed the 28 day DLT evaluation point before the 4th subject will begin treatment.

IRX5183 will be initiated at the company’s currently recommended dosage for use in APL patients of 50 mg daily (about 30 mg/m^2/day). The drug is available in 25 mg capsules, so we will be using a flat dosage. This dose of 50 mg is above the MTD of 15 mg/m^2/day from the prior phase I trial conducted in solid tumor patients. However, the DLTs seen in this trial were elevations in alkaline phosphatase in patients with known liver metastases. In addition, the phase I/II trial in patients with myeloma and lymphoma used a dose of 60 mg/m^2, which was well tolerated with no serious adverse events (SAEs). The roughly 2 months of induction therapy followed by consolidation/maintenance described above is modeled after prior studies of ATRA and other synthetic retinoids, in which it can take up to 60 days to see an initial response (Lo-Coco et al., 2013; Sanford D, 2014; Tobita et al., 1997).

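### Phase II has no numerical toxicity boundary: a dose cleared on six patients is expanded on unquantified judgement, and the only formal look tests response

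*Combined protocol and SAP*

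**What the plan says.** **Clearing the dose.** Section 5.1 (Study Phase I) says the RP2D will generally be "the highest dose at which the DLT rate is <33% in at least six patients". Table 2 in section 5.2 makes this fewer than 2 DLTs among 6 patients. Section 5.2 defines a DLT for dose escalation, over the first 28 days of therapy.

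**Exposure after clearance.** Section 11.4 plans 27 patients at the RP2D, including those treated at that dose in phase I, so 21 are new. It adds 8 for dropout, up to 35.

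**Continuing phase II.** Section 11.4 says "the study team will meet regularly to determine whether it is worthwhile to continue enrollment" when an unspecified excess of patients cannot complete two cycles, because of either DLTs or progression. The formal interim rule in section 11.1 concerns response: "Stage 1 will enroll 13 patients at the RP2D and will require at least 1 response". Section 5.1 (Study Phase II) describes the same pause: "We will halt enrollment after the first 13 patients complete induction therapy until we have their response data".

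**Early toxicity failures.** Section 11.8.2 states that "death due to toxicity prior to completion of induction therapy will be excluded from the primary analysis", and that patients who do not complete induction are replaced until 27 is reached.

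**Other safeguards.** Section 7.6 puts the trial on hold for unexpected and serious toxicity that creates unacceptable risk. Section 5.2 provides for a review of the design if chronic toxicity appears. Section 12 gives the PI ongoing monitoring, with annual committee review. Section 6 sets patient-level holds, modifications and discontinuations. Section 11.8.1 keeps every treated patient evaluable for toxicity.

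**The concern.** The protocol has a numerical toxicity limit, but uses it only to choose the RP2D. After that, most of the exposure at the chosen dose accrues under provisions with no count or rate attached. Three features make this matter.

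- Six patients say little about a DLT rate, so a dose at or above the protocol's own limit can pass by chance.
- The hold in section 7.6 is for unexpected toxicity. It does not clearly cover an expected retinoid toxicity that occurs too often.
- Section 11.4 pools DLTs with progression. In relapsed or refractory disease, early progression can mask a high DLT rate, or be mistaken for one.

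Section 11.4 also uses DLT as a phase II reason for non-completion, although section 5.2 defines the term only for escalation. At stake is how soon an intolerable dose would be recognised during the expansion.

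**Working it through.** **1. The plan's own design.** Inputs from section 11.1: "based upon a Type I error rate of 0.05, power of 0.8, response probability of poor drug 0.05", "response probability of good drug of 0.2", stage 1 of 13 patients, and "A total of 4 or more responses out of 27 patients will be considered encouraging evidence". The chance of declaring the drug encouraging is Σ (x = 1 to 13) P(X₁₃ = x) × P(X₁₄ ≥ 4 − x).

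- At p = 0.05 this is 0.0416.
- At p = 0.20 it is 0.801.
- The chance of stopping early at p = 0.05 is 0.95¹³ = 0.513.

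The design reproduces. Both of its decision rules use response counts only.

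**2. What six patients establish.** A dose tested in six patients clears if it has 0 or 1 DLT: P = (1 − p)⁶ + 6p(1 − p)⁵.

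| True DLT rate | P(clears) |
|---|---|
| 20% | 0.262 + 0.393 = 0.66 |
| 33% | 0.090 + 0.267 = 0.36 |
| 40% | 0.047 + 0.187 = 0.23 |
| 50% | 0.016 + 0.094 = 0.11 |

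The exact two-sided 95% upper limit for the DLT rate is 64% after 1/6 and 46% after 0/6.

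**3. Further exposure.** New patients number 27 − 6 = 21, or 35 − 6 = 29 if the 35 also includes the phase I six. At a true rate of 1/3, the expected further DLTs are 21/3 = 7 or 29/3 = 9.7. At up to 3 patients a month (section 11.5), accrual takes about 7 to 10 months plus the pause at 13. Most of it could therefore fall between two annual reviews.

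**4. What the response look can see.** The look uses the first 13 patients who complete induction. A patient who dies of toxicity before then is not among them and is replaced, so the event is not counted even as a non-response.

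**5. An illustrative boundary.** The documents set no tolerable rate for phase II, so these settings are assumptions:

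- limit 0.33, taken from section 5.1
- Beta(1,2) prior
- hold when Pr(DLT rate > 0.33) ≥ 0.80
- looks every 3 patients, with the phase I six counted

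With x DLTs in n patients the posterior is Beta(1 + x, 2 + n − x). The rule holds at 5/9, 6/12, 7/15, 8/18, 9/21, 11/24, 12/27, 13/30 or 14/33 or more. The 9/21 entry is marginal: its posterior probability is 0.803 at a limit of 0.33 but 0.794 at 1/3, where the cut-off becomes 10/21.

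P(hold), given 0 or 1 DLT in the first six:

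| True DLT rate | Looks through 24 | Through 27 | Through 33 |
|---|---|---|---|
| 20% | 0.5% | 0.5% | 0.6% |
| 33% | 9% | 10% | 12% |
| 40% | 23% | 26% | 33% |
| 50% | 53% | 59% | 71% |

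**6. Sensitivity to the tolerable rate.** A boundary checked after each patient, referenced to 20% with at most 10% stopping at that rate, holds at 4/6, 6/13, 8/20 and 10/27, among other points. Given clearance on six, it stops by 27 patients with probability 2% at a true 20%, 27% at 1/3, 50% at 40% and 82% at 50%. The choice of rate drives the result.

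**The case against.** A reader might infer that phase II has no safety trigger at all. The documents do not support that. Besides the provisions above, section 7.7 requires SAE reports within 24 hours and section 13.6 promises frequent analysis for safety. What is missing is a number.

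A reader might also infer that toxicity deaths disappear from the trial. They do not. Section 11.8.1 keeps them evaluable for toxicity, section 11.7 tabulates toxicities and promises a response section on all eligible patients, and the exclusion applies to the primary response analysis. A Simon response rule is not meant to be a safety monitor, so its blindness to toxicity is not a separate defect. It means only that the response look cannot stand in for one.

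The strongest remaining objection is that the gain is modest. Clearing and then being held, with looks through 24, has joint probability 0.358 × 0.092 = 3% at 33%, 0.233 × 0.230 = 5% at 40% and 0.109 × 0.528 = 6% at 50%. Given clearance, that version misses about 91% of doses at exactly 33%. This stands: the illustrative rule mainly guards against rates well above the limit. The limit, prior, threshold and look schedule are also choices that the documents do not make.

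**Conclusion.** The point holds as the absence of a numerical phase II toxicity boundary, not as an absence of oversight. A dose at a true DLT rate of 33% to 50% clears the six-patient test with probability 0.36 to 0.11, and nothing countable then governs the next 21 to 29 patients. It is a cheap improvement rather than a flaw that invalidates the design.

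The figures assume independent patients with a constant DLT rate, and outcomes known at each look. The clearance probabilities apply to a dose tested in six patients. They are not the probability that escalation selects that dose. Exposure of 21 to 29 follows section 11.4. Section 5.1 (Study Phase II) can be read as recruiting 27 in phase II itself, and the two should be reconciled.

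**What to change.** Add to section 11.4 a numerical rule that suspends enrolment for safety review.

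- Count every patient treated at the RP2D, including the phase I patients and anyone later replaced.
- State that the section 5.2 DLT definition applies to phase II monitoring. Its 28-day window covers only half of the 56-day induction, so say how cycle 2 toxicity will be reviewed.
- Count DLTs separately from progression.
- Run the looks through 33, so that accrual up to 35 is covered.
- Say whether enrolment continues while a group completes its 28 days. At 3 patients a month, about three could be in that window.

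The boundary in step 5 of the working is an illustration. The tolerable rate and the threshold are for the sponsor and investigator to confirm, and the limit should be written as either 0.33 or 1/3 because the cut-off at 21 depends on it.

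The cost is a protocol amendment, DLT classification in phase II from toxicity data already collected, and a chance of an unnecessary pause of about 0.5% at a true rate of 20%. The 13/27 design and the threshold of 4 responses stay as they are.
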